### **10.2.3. Missing Data**

Analyses will be based on observed data only; no data will be imputed.

### **10.2.4. Disposition of Patients**

Patients who are screened for study entry and do not meet the eligibility criteria will be documented. The numbers and proportions of patients who complete the study and who are early terminations will be summarized. Reasons for study discontinuation after the start of study treatment will be tabulated.

### **10.2.5. Demographics and Baseline Characteristics**

Demographic and baseline disease characteristic data will be summarized. Data to be tabulated will include demographic and baseline characteristics such as sex, age, race, height, weight, and body mass index, and MM-specific diagnostic and historical information. Medical history will be coded using Medical Dictionary for Regulatory Activities (MedDRA) and raw and coded data will be summarized.

#### **10.2.6. Extent of Exposure**

Descriptive statistics for the percent of expected dose received and the actual dose received will be summarized. A tabular summary and listing of drug administration and dose level, and a by-patient listing of the date and time of each study drug dose and the dose administered also will be presented.

#### **10.2.7. Prior and Concomitant Medications**

Tabulations of prior and concomitant medications, coded using the World Health Organization Drug Dictionary (WHO-DD), will be produced. All prior and concomitant medications administered will be presented in a data listing.

#### **10.2.8. Efficacy Analyses**

Superiority testing will be performed on FAS in the Phase 2 cohort to investigate the null hypothesis that the primary endpoint of responder rate is below or equal to the gold standard against the alternative hypothesis that it is higher than the gold standard. The gold standard is assumed to be 77.5% (CIBMTR report, December 2017) and a 1-sided 2-step chi-square test will be performed at the 2.5% level of significance for FAS.

For the primary endpoint, also an upper 1-sided 97.5% confidence interval will be calculated for FAS in addition to summary statistics.

For the primary endpoint in other sets and for the secondary endpoints of other responder rates in the FAS, also 2-sided 95% confidence intervals will be calculated in addition to summary statistics.

Response assessments as determined by the Investigator and IRC will be compared, with agreement determined by Kappa coefficient.

Disease assessment variables and their changes from baseline will be summarized visit wise.

#### **10.2.9. Pharmacokinetic Analyses**

PK analysis for tinostamustine and its metabolites will be performed using the PK set.

PK parameters at all doses will include  $C_{max}$ , time to maximum plasma concentration ( $t_{max}$ ),  $t_{1/2}$ , area under the plasma concentration curve from 0 to 12 hours ( $AUC_{0-12}$ ), area under the plasma concentration curve from time 0 to time t ( $AUC_{0-t}$ ), apparent total clearance (CL/F), apparent volume of distribution (Vd/F), and terminal disposition rate constant ( $\lambda_z$ ). The initial calculation of PK parameters will be performed using non-compartmental analysis. Plasma concentrations and PK parameters will be summarized by dose.

Summaries will include the number of observations (n), arithmetic or geometric mean, SD or coefficient of variation (CoV), median, minimum, and maximum.

#### **10.2.10. Safety Analyses**

Safety data, including changes from baseline, if applicable, will be summarized at each dose level for the safety set.

Adverse Events will be coded using MedDRA and raw and coded data will be summarized.

Additional safety analyses may be determined at any time without prejudice, in order to enumerate rates of toxicities most clearly, and to define further the safety profile of tinostamustine.

#### **10.2.11. Interim Analyses**

In Phase 2 of the study, at the completion of the Stage 1 with 31 patients, an interim analysis will be performed using the FAS for the Phase 2 cohort to determine whether enrollment will continue in Stage 2. If  $>25$  of 31 patients in Stage 1 experience a response to treatment, then enrollment will continue in Stage 2, with up to 40 patients planned to be enrolled. However, if  $\leq 25$  patients in Stage 1 experience a response to treatment, no further patients will be enrolled in the ongoing Stage 2 recruitment.

### **10.3. Changes to the Planned Statistical Methods**

Changes to the planned statistical methods will be documented in the clinical study report.

## **11. ETHICAL, LEGAL, AND ADMINISTRATIVE CONSIDERATIONS**

### **11.1. Good Clinical Practice**

This study will be conducted according to the protocol and in compliance with ICH GCP, the ethical principles stated in the Declaration of Helsinki, and other applicable regulatory requirements.

The Investigator confirms this by signing the protocol.

### **11.2. Informed Consent**

Written informed consent will be obtained from each patient prior to undergoing any protocol-specific tests or procedures that are not part of routine care.

The Sponsor or designee will provide an ICF template to the Investigator for use in developing a study center-specific consent documents. Prior to submission of the study center-specific ICF to the IRB/EC, these documents must be reviewed and approved by the Sponsor or designee. Any changes requested by the IRB/EC must also be approved by the Sponsor or designee. The final IRB/EC-approved ICF must be provided to the Sponsor or designee. Revisions to the ICF required during the study must be approved by the Sponsor or designee, and a copy of the revised ICF provided to the Sponsor or designee.

Before recruitment and enrollment, each prospective patient will be given a full explanation of the study and be allowed to read the ICF in a language they understand. After the Investigator or designee is assured that the patient understands the commitments of participating in the study, the patient will be asked to sign and date the ICF, as appropriate.

A copy of the fully signed and dated ICF will be given to the patient. The original will be maintained in the patient's medical record at the study center. All active patients will sign an updated ICF if revisions are made to the ICF during the course of the study.

### **11.3. Institutional Review Board/Ethics Committee**

Federal and European regulations and ICH require that approval be obtained from an IRB/EC prior to participation of patients in research studies. Approval by the Competent Authority, if applicable, or as required by local laws and regulations, is also required in Europe. Prior to the study onset, the protocol, any protocol amendments, ICFs, advertisements to be used for patient recruitment, and any other written information regarding this study to be provided to a patient or patient's legal guardian, must be approved by the IRB/EC.

All IRB/EC approvals must be dated and signed by the IRB/EC Chairperson or designee and must identify the IRB/EC by name and address, the clinical protocol by title and/or protocol number, and the date approval or favorable opinion was granted for the clinical research.

No drug will be released to the site to dose a patient until written IRB/EC authorization has been received by the Sponsor or designee.

The Investigator is responsible for obtaining continuing review of the clinical research at least annually or more often if specified by the IRB/EC. The Investigator must supply the Sponsor or designee with written documentation of the approval of the continued clinical research.

The Investigator, sponsor, or designee as applicable, will make all attempts to ensure that the IRB/EC is constituted and operates in accordance with Federal and ICH GCP and any local regulations.

#### **11.4. Amending the Protocol**

Any changes in this research activity, except those to remove an apparent immediate hazard to the patient, must be reviewed and approved by the Sponsor or designee and the IRB/EC that approved the study. Amendments to the protocol must be submitted in writing to the Investigator's IRB/EC for approval prior to patients being enrolled into the amended protocol.

The Sponsor may make administrative changes (i.e., changes that do not significantly affect patient safety or the study's scope or scientific quality) without any further approvals.

All amendments will be distributed to all protocol recipients.

#### **11.5. Confidentiality**

All study findings and documents will be regarded as confidential. The Investigator and other study personnel must not disclose such information without prior written approval from the Sponsor.

Patient confidentiality will be strictly maintained to the extent possible under the law. Patient names must not be disclosed. Patients will be identified in the eCRFs and other documents submitted to the Sponsor or its designated representative, by their initials, birth date, and/or assigned patient number. Documents that identify the patient (e.g., the signed ICF) should not to be submitted to the Sponsor or its designated representative, and must be maintained in confidence by the Investigator.

#### **11.6. Publication Policy**

It is anticipated that the results of this study will be presented at scientific meetings and/or published in a peer reviewed scientific or medical journal. The initial planned publication will be a multicenter report of the study outcome. Additional publications from a given center can only occur after the publication of the multicenter results. A prepublication manuscript is to be provided to the Sponsor at least 30 days prior to the submission of the manuscript to a publisher. Similarly, the Sponsor will provide any company-prepared manuscript to the Investigators for review at least 30 days prior to submission to a publisher.

## **12. STUDY MANAGEMENT**

### **12.1. Data Quality Assurance**

The Sponsor or its designated representative will conduct a study center visit to verify the qualifications of each investigator, inspect study center facilities, and inform the Investigator of responsibilities and procedures for ensuring adequate and correct study documentation.

### **12.2. Case Report Forms and Source Documentation**

The Investigator and designees agree to maintain accurate eCRFs and source documentation as part of case histories. Source documents are the originals of any documents used by the Investigator or subinvestigator or hospital/institution that allow verification of the existence of the patient and substantiate the integrity of the data collected during the study.

The Sponsor or designee will provide eCRFs to the study center. eCRFs will be completed for each patient. It is the Investigator's responsibility to ensure the accuracy, completeness, and timeliness of the data reported in the patient's eCRF. Source documentation supporting the eCRF data should indicate the patient's participation in the study and should document the dates and details of informed consent, study procedures, AEs, and patient status.

The Investigator, or designated representative, should complete the eCRF as soon as possible after information is collected/data are available, preferably on the same day that a patient is seen for an examination, treatment, or any other study procedure. Any outstanding entries must be completed immediately after the final examination. An explanation should be given for all missing data.

The Investigator must sign and date the Investigator's Statement at the end of the eCRF to endorse the recorded data.

### **12.3. Monitoring**

A CRA, or other representative of the Sponsor, will conduct a study center visit to verify the qualifications of each Investigator, inspect study center facilities, and inform the Investigator of responsibilities and procedures for ensuring adequate and correct study documentation.

During the course of the study, the CRA will make study center visits to review protocol compliance, compare eCRFs and individual patients' medical records, assess drug accountability, and ensure that the study is being conducted according to pertinent regulatory requirements in respect to GCP. eCRFs will be verified with source documentation. The review of medical records will be performed in a manner to ensure that patient confidentiality is maintained.

### **12.4. Inspections**

Regulatory authorities and/or quality assurance personnel from the Sponsor or its designated representative, may wish to carry out such source data checks and/or in-center audit inspections.

The Investigator assures the Sponsor of the necessary support at all times. In the event of an audit, the Investigator agrees to allow the sponsor's representatives and any regulatory agencies access to all study records.

## **12.5. Financial Disclosure Reporting Obligations**

Investigators and subinvestigators are required to provide financial disclosure information to the sponsor to permit the sponsor to fulfill its regulatory obligation. Investigators and subinvestigators must commit to promptly updating the information if any relevant changes occur during the study and for a period of 1 year after the completion of the study.

## **12.6. Archiving Study Records**

Essential documents should be retained for a minimum of 2 years after the last approval of a marketing application in an ICH region and until there are no pending or contemplated marketing applications in an ICH region or at least 2 years have elapsed since the formal discontinuation of clinical development of the investigational product. However, these documents should be retained for a longer period if required by the applicable local requirements.

ICH requires that patient identification codes be retained for at least 15 years after the completion or discontinuation of the study.


Storer BE. Design and analysis of phase I clinical trials. *Biometrics* 1989;45(3):925-37.

**Date:** September 21, 2018

**To:** EDO-S101-1004 (TITANIUM 1) Investigators and Site Staff

**Protocol Title:** A Phase 1/2 Open-Label Trial of Tinostamustine Conditioning and Autologous Stem Cell Transplant for Salvage Treatment in Relapsed/Refractory Multiple Myeloma (TITANIUM 1)

**Protocol Version:** 2.0, 18 June 2018

**Subject:** Protocol Clarification Memo

---

Dear Investigators and Site Staff,

Please see below clarifications for EDO-S101-1004 version 2.0 protocol from 18 June 2018.

**Item 1:** Use of central line

Currently, Protocol Version 2.0 18 June 2018 states on the bottom of page 11, that Tinostamustine will be administered by IV infusion through a peripheral vein over 1 hour. This is also noted in section 7.6.2 on page 49.

It should say that Tinostamustine will be administered by IV infusion through a peripheral vein or a central line over 1 hour.

**Item 2:** Day of Autologous Stem Cell Transplant (ASCT)

Currently, Protocol Version 2.0 18 June 2018 states in the header of the Schedule of Events on pages 17 and 18, that ASCT is on Day 0.

It should say that the day of ASCT is study Day 1.

**Item 3:** Exclusion Criteria #2

Currently, Protocol Version 2.0 18 June 2018 has two Exclusion Criteria #2's listed on page 39. The one noted as "Primary or secondary plasma cell leukemia at any point prior to transplant" is not noted in the Clinical Study Synopsis exclusion criteria list on page 10.

This exclusion criteria should be included in the Clinical Study Synopsis.

#### **Item 4 Protocol Deviations**

Currently, Protocol Version 2.0 18 June 2018 states that all protocol deviations and reasons for such deviations must be noted in the eCRF.

It should say that all protocol deviations and reasons for such deviations must be noted in the CTMS.

#### **Item 5 Confirmatory Response Assessment**

Currently, Protocol Version 2.0 18 June 2018 states on pages 12 and 42 that a confirmatory response assessment will be done between D107 and D130. On the schedule of assessments on pages 17 and 18, it is listed as D130 (+/-7 days).

It should say that a confirmatory response assessment will be done between D107 and D130, ideally approximately 4 weeks after the initial evaluation.

#### **Item 6 Discharge Criteria**

Currently, Protocol Version 2.0 18 June 2018 states on pages 6 and 37 that the following engraftment criteria need to be met in order for the patient to be discharged:

- Neutrophil engraftment is defined as the first of 3 consecutive days with ANC  $>0.5 \times 10^9/L$ .
- Platelet engraftment will be defined as the first 3 consecutive days of platelet count  $>20 \times 10^9/L$  without platelet transfusion in the prior 7 days.

It should say the following:

- Absolute neutrophil count  $>0.5 \times 10^9/L$ .
- Patient is not platelet transfusion dependent.

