**Table 1: Schedule of Events (Phases 1 and 2)**

Procedure	Screening	Conditioning	ASCT	Post-ASCT Follow-up 			
	D-28 to -1	D-1	D0	M1	M2	D100 (±7 days)	D130 (±7 days)
Written informed consent 	X						
Eligibility review	X		X				
Demographics	X						
Medical history	X						
HCT-CI	X						
Cancer history, including history of prior ASCT and other treatments	X						
ECHO or MUGA scan	X						
Pulmonary function testing 	X						
Infectious disease screening 	X						
Pregnancy test 	X						
ECOG performance status	X		X	X	X	X	
Complete physical examination	X						
Targeted physical examination		X	X	X	X	X	
Height	X						
Weight	X		X	X	X	X	
Vital signs 	X	X	X 	X	X	X	
Continuous Holter monitoring		X 					
12-lead ECG 	X 	X 		X			
Hematology 	X	Repeat daily until hospital discharge					
Kidney function tests (creatinine, urea, and uric acid)		Daily from the start of tinostamustine through Day 3 post-ASCT					

*CONFIDENTIAL*

Procedure	Screening	Conditioning	ASCT	Post-ASCT Follow-up 			
	D-28 to -1	D-1	D0	M1	M2	D100 (±7 days)	D130 (±7 days)
Clinical chemistries 	X	X	X	X	X	X	
Coagulation parameters: PT and/or INR, aPTT	X		X	X		X	
Urinalysis 	X						
Tinostamustine administration 		X					
PK sample collection		X 					
ASCT 			X				
Disease assessments							
Skeletal survey 	X						
Bone marrow aspirate and biopsy 	X					D100 (±7 days) 	
Serum / urine M protein quantitation	X			X	X	X	X
Immunoglobulin quantitation (IgA, IgG, and IgM [required]; IgD, IgE [optional])	X			X	X	X	X
Free light chain analysis	X			X	X	X	X
Disease response assessment 	X			X	X	X	
Evaluation for MRD-N						D100 (±7 days) 	
AE monitoring 	AEs, including SAEs, are to be documented from the provision of written informed consent through Day 100.						
Prior/concomitant medications 	All medications administered within 28 days before Day 1 through Day 100 are to be documented.						

1. Patients will be evaluated daily on an inpatient basis until engraftment criteria are met and the patient is discharged from the hospital. Thereafter, study center visits will be performed on an outpatient basis. Visit M1: D30 (±5days); visit M2: D60 (±5days)

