### **3.2.2. Safety**

The safety endpoint in Phase 1 of the study is:

- DLTs

Additional safety endpoints in both Phases 1 and 2 of the study are:

- Incidence of neutrophil and platelet engraftment failure.
- Duration of cytopenia (i.e., absolute neutrophil count [ANC]  $\leq 0.5 \times 10^9/L$ ; platelet count  $\leq 20 \times 10^9/L$ ).
- Cumulative incidence of treatment-related mortality (TRM).
- Transplant-related non-hematologic Grade 3 toxicity over time through Day 30, stratified by hematopoietic cell transplantation comorbidity index (HCT-CI).
- Incidence of adverse events (AEs) and serious adverse events (SAEs).
- Change from baseline in standard safety hematology and clinical chemistry test results.

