### **6.2. Patient Management**

All patients must provide written informed consent before any samples are collected or evaluations performed in this study that are not part of standard patient care. Patients will be evaluated for study eligibility during the Screening period, within 28 days before baseline (Day 1; the Day of ASCT).

Patients who are determined to be eligible, based on Screening assessments, will return to the clinic to receive the tinostamustine conditioning regimen; the tinostamustine dose will be administered 24 hours pre-ASCT (on Day -1).

On Day 1, ASCs will be administered IV according to standard institutional practice.

During in-patient hospitalization, patients will be assessed daily for toxicity through Month 1 Day 30 ( $\pm 5$  days) post-ASCT or until all transplant-related toxicity resolves. Patients will be discharged from the study center once engraftment criteria are met (see [Section 8.3](#)).

Thereafter, patients are to be followed at Month 2 Day 60 ( $\pm 5$  days) and Day 100 ( $\pm 7$  days).

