### **8.3. Engraftment**

During in-patient hospitalization, patients will be assessed daily for hematologic engraftment, starting on the first day the ANC is  $<0.5 \times 10^9/L$  until and including the day engraftment criteria are met, as follows:

- Neutrophil engraftment is defined as the first of 3 consecutive days with ANC  $>0.5 \times 10^9/L$ .
- Platelet engraftment will be defined as the first of 3 consecutive days of platelet count  $>20 \times 10^9/L$  without platelet transfusion in the prior 7 days.

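### A memo allows discharge before the engraftment definitions are met, but scheduled blood counts still stop at discharge, so platelet engraftment in particular can go undocumented

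*Protocol*

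**What the plan says.** **Definitions.** Section 8.3 of protocol version 2.0 reads "Neutrophil engraftment is defined as the first of 3 consecutive days with ANC" above 0.5 × 10⁹/L. For platelets it reads "Platelet engraftment will be defined as the first of 3 consecutive days of platelet count" above 20 × 10⁹/L, with no platelet transfusion in the preceding 7 days.

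**Uses.** Section 3.2.2 lists "Incidence of neutrophil and platelet engraftment failure" and duration of cytopenia as safety endpoints in both phases. Section 7.5.2 makes failure to meet both criteria within 30 days of ASCT a dose-limiting toxicity if it is considered at least possibly related to tinostamustine. Section 7.5.1 uses engraftment without Grade 3 or higher toxicity as one of two ways to release further enrollment; the other is 30 days without a DLT.

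**Collection.** The hematology row of Table 1 has a screening mark and then "Repeat daily until hospital discharge". Nothing is marked at M1, M2, Day 100 or Day 130, whereas clinical chemistry is marked at M1, M2 and Day 100. Section 8.3 opens with "During in-patient hospitalization, patients will be assessed daily for hematologic engraftment", although the same sentence sets its end at the day the criteria are met.

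**Discharge.** In version 2.0, Section 6.2 has patients "discharged from the study center once engraftment criteria are met", and the synopsis and Section 4.1 agree. Memo Item 6 replaces this with "Absolute neutrophil count" above 0.5 × 10⁹/L and "Patient is not platelet transfusion dependent". It has no three-day run, no platelet threshold and no transfusion-free interval, and it does not define dependence.

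**The concern.** Stopping counts at discharge was adequate only because discharge itself required engraftment. The memo removes that requirement and leaves the collection schedule, the engraftment definitions, the endpoints and the DLT as they were. A patient can therefore leave hospital, within the rules, before the data needed to classify them have been collected.

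This reaches beyond summary tables. The first patient of the initial cohort and the last patient of each cohort must clear the engraftment or 30-day condition before enrollment moves on. If engraftment cannot be shown from protocol-required counts, that decision rests on whatever counts the site happens to have.

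**Working it through.** There is no sample size or power figure to reproduce. The check sets the rules side by side and counts days.

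**1. Is the blank in Table 1 real?** Version 1.0 has the same hematology row with the same empty follow-up columns, so an extraction fault is unlikely. None of the four clarification memos (September, October and December 2018, January 2019) adds a count after discharge.

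**2. Which passages did Item 6 change?** It names only pages 6 and 37, the synopsis and Section 4.1.
- Section 6.2 still ties discharge to engraftment.
- Table 1 footnote 1 still ties in-patient evaluation to engraftment and discharge together.
- Section 8.3 still combines an in-patient condition with an engraftment end point.
- The December 2018 memo drafts risk-benefit text describing daily hematologic evaluation up to engraftment, without altering Table 1.

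The memo rule and these passages cannot all be followed for a patient discharged before engraftment.

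**3. Neutrophils.** Let d be the first day with ANC above 0.5.
- Memo discharge is possible on day d.
- The definition needs days d, d+1 and d+2.
- Days that can fall after discharge: (d+2) − d = 2.

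Neutropenia is defined by ANC ≤0.5, with no three-day rule, so the end of the first neutropenic interval is seen on or before discharge. The candidate engraftment date, d, is also seen. Only the confirmation can be missing.

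**4. Platelets.** Let t be the day of the last platelet transfusion.
- The first day with no transfusion in the prior 7 days is t+7 or t+8, depending on how the interval is counted.
- If the count is above 20 from that day, the three-day run ends 2 days later, at t+9 or t+10. If the count recovers later, the run ends later.
- For discharge on day t+k, the days still outstanding are 9−k to 10−k. As an illustration, k = 3 leaves 6 to 7 days.

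The memo sets no interval and no count, so nothing in it fixes k. Part or all of the window can fall after discharge. A patient who leaves with platelets ≤20 has no later scheduled count to close the cytopenia interval.

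**5. The 30-day DLT.** M1 is Day 30 ± 5, so Day 25 to Day 35. It has chemistry but no hematology mark. A patient discharged with a criterion unconfirmed therefore has no scheduled count near Day 30.

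**6. What the SAP does with these data.** SAP Section I.C states that the DLT, engraftment-failure, cytopenia-duration and hematology change-from-baseline analyses are no longer applicable after the safety halt. SAP Section VIII.B keeps a listing of engraftment data as entered on the eCRF. Engraftment failure remains an end-of-study reason in Section VI.B, and DLT type remains in the adverse-event listing in Section VIII.A.

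**The case against.** The best defence is that several passages still aim at engraftment: the end of the Section 8.3 sentence, Section 6.2, Table 1 footnote 1 and the later December 2018 text. Section 9.2.7.1 also lets investigators repeat laboratory tests as needed, and engraftment has its own eCRF record. This stands in part. Counts may well exist for many patients, and the accurate description is a conflict between passages. But none of this text schedules a count after discharge, discretionary tests are not required data, and an eCRF engraftment entry still needs counts behind it.

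Some stronger readings are tempting but are not supported:
- *The endpoints become unobservable.* Not in general. The end of first neutropenia is observed, and discretionary counts may fill the platelet gap.
- *Dates are wrong by about two weeks.* If one assumed discharge on Day 14 to 20 and dating at M1, the gap would run from 25 − 20 = 5 to 35 − 14 = 21 days. The documents give no discharge day, and M1 has no scheduled count from which to date anything.
- *The loss is informative.* It may be, but this is not shown. Patients without neutrophil recovery, or who are transfusion dependent, do not meet the memo criteria and so stay under daily counts. They are the likeliest engraftment failures.
- *The memo damages hematology change from baseline.* Version 2.0 already ended scheduled hematology at discharge, so this is not an effect of the memo.
- *The SAP dropped the analyses because counts were missing.* The SAP attributes this to the safety halt.

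**Conclusion.** The point holds as a mismatch between the memo's discharge rule and the collection schedule. For patients discharged under Item 6 before the definitions are met, up to two confirming neutrophil days and part or all of the platelet window lie beyond the last scheduled count. The exposure is mainly platelet engraftment, duration of platelet cytopenia and confirmation of neutrophil engraftment.

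This rests on two assumptions: that sites follow Item 6 and Table 1 as written, and that no discretionary counts are entered. How many patients would be affected, and by how many days, cannot be derived from the documents.

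The consequence for the final report is small, since the affected analyses were withdrawn and mainly listings remain. The gap matters for trial conduct, above all for the delayed-engraftment DLT and the release of cohorts while the memo was in force. It is a cheap improvement and does not invalidate the plan.

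**What to change.** 1. Reconcile memo Item 6 with Table 1 and its footnote 1, Section 6.2, Section 8.3 and the December 2018 memo text. Which discharge rule applies is for the sponsor and investigators; no view is taken here.
2. End the collection of blood counts and platelet transfusion dates in the eCRF when both engraftment criteria are documented, not at discharge. Counts taken in routine care after discharge can be entered.
3. Mark hematology at M1, where blood is already drawn for chemistry. Add it at M2 and Day 100 only if a criterion is still undocumented. One M1 count cannot show a three-day run, so it backs up step 2 and does not replace it.
4. In the engraftment listing under SAP Section VIII.B, flag patients discharged before both criteria were documented.

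The cost is a little extra data entry and one added blood count on an existing sample.
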